- Treatment Phase:** Tumor assessments of the neck (DTC only), chest, and other areas of known disease at Screening or newly suspected disease should be performed every 8 weeks (within week 8) from C1D1 during the Treatment Phase (or sooner if there is evidence of progressive disease) and should use the same methodology (CT or MRI) and scan acquisition techniques (including use or nonuse of IV contrast) as was used for the screening assessments. Tumor response will be assessed according to RECIST 1.1. An initial assessment of CR or PR must be confirmed not less than 4 weeks after achievement of the initial response. After treatment discontinuation, tumor assessment should continue to be performed every 8 weeks until documentation of progression for 1 year or start of a new anticancer agent (refer to [Section 9.5.1.3](#)).
- p. Brain CT with contrast or MRI pre- and post- gadolinium contrast will be performed at the Screening Visit, and as clinically indicated. For subjects with protocol-eligible treated brain metastases, brain CT/MRI will be performed at all tumor assessment time points.
- q. Height will be assessed at the Baseline Visit, Day 1 of every 3 cycles during the Treatment Phase, at the Off-treatment Visit, and every 3 months during the Post-treatment Follow-up. Proximal tibial growth plates x-rays should be conducted at baseline, and at the Off-treatment visit.
 - r. Blood samples will be collected at the Baseline Visit, C1D15, Day 1 of all subsequent cycles, at the Off-treatment Visit for blood serum sample to measure factors implicated in angiogenesis. For subjects ongoing after the data cutoff date for the primary analysis, blood samples will be collected at the Off-Treatment Visit.
- s. An archival tumor sample from the most recent surgery or biopsy for identification of predictive biomarkers and pathology review may be collected at any time during the study, unless no such material is available.
- t. Collection of whole blood to obtain genomic DNA will be performed at the Baseline Visit. If sampling is not performed predose, sampling may occur at any subsequent visit in which other blood sampling is scheduled to occur. Pharmacogenomic markers of drug metabolism and drug transport may be assessed.
- u. Survival data will be collected every 3 months until death or 1 year as per the protocol. All anticancer therapies will be collected.

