Treatment Phase: Tumor assessments of the chest, and other areas of known disease at Screening or newly suspected disease should be performed every 6 weeks (within Week 6) from C1D1 during the Treatment Phase (or sooner if there is evidence of progressive disease) and should utilize the same methodology (CT or MRI) and scan acquisition techniques (including use or nonuse of IV contrast) as was used for the screening assessments. Tumor response will be assessed according to RECIST 1.1. Subjects who discontinue must complete the off-treatment tumor assessment. Any CR or PR must be confirmed not less than 4 weeks following the initial achievement of the response. After treatment discontinuation, tumor assessment should continue to be performed every 6 weeks until documentation of progression for 1 year or start of a new anticancer agent (refer to [Section 9.5.1.3](#)).
- p. Brain CT with contrast or MRI pre- and post- gadolinium contrast will be performed at the Screening Visit, and as clinically indicated. For subjects with protocol-eligible treated brain metastases, brain CT/MRI will be performed at all tumor assessment time points.

- q. Height will be assessed at the Baseline Visit, Day 1 of every 3 cycles during the Treatment Phase, at the Off-treatment Visit and every 3 months during the Post-treatment Follow-up for 1 year. Proximal tibial growth plates x-rays should be conducted at baseline and at the Off-treatment Visit. Hand and wrist x-rays and tibial growth plate x-rays will be optional for Germany.
- r. Blood samples will be collected at the Baseline Visit, C1D8, Day 1 of all subsequent cycles, and at the Off-Treatment assessment for blood serum sample to measure factors implicated in angiogenesis. For subjects ongoing after the data cutoff data for the primary analysis, blood samples will be collected at the Off-Treatment Visit.
- s. An archival tumor sample from the most recent surgery or biopsy for identification of predictive biomarkers and pathology review may be collected at any time during the study, unless no such material is available.
- t. Collection of whole blood to obtain genomic DNA will be performed at the Baseline Visit. If sampling is not performed predose, sampling may occur at any subsequent visit in which other blood sampling is scheduled to occur. Pharmacogenetic markers of drug metabolism and drug transport may be assessed.

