12 APPENDICES

Appendix 1 **Response Evaluation Criteria in Solid Tumors (RECIST) 1.1**

Tumor response assessments in this clinical trial will use Response Evaluation Criteria in Solid Tumors (RECIST 1.1) based on the 2009 article by Eisenhauer et al entitled *New Response Evaluation Criteria in Solid Tumors: revised RECIST guideline (version 1.1)* ([Eisenhauer, et al., 2009](#)).

The sole modification to RECIST 1.1 to be implemented in this trial is that chest x-rays may not be used to follow disease; only CT scans may be used to follow chest disease. As required by RECIST 1.1, the protocol states that the minimum duration of stable disease is 7 weeks following the date of first dose of study drug.

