5.1.2 Secondary Endpoints

- Efficacy endpoints:

- BOR over the treatment period (except for Cohort 2A): defined as the best response recorded from the start of study drug until 30 days after the last dose or until PD, whichever occurs earlier
- ORR (except for Cohort 2A): defined as the proportion of subjects who have BOR of CR or PR
- DOR: defined as the time from first documentation of tumor response (CR or PR) to PD
- Disease Control Rate (DCR): defined as the percentage of subjects with measurable disease who have a BOR of CR or PR or stable disease (SD) or subjects with evaluable disease who have a BOR of CR or Non-CR/Non-PD. To be assigned a BOR of SD or Non-CR/Non-PD, the time from the first administration of study drug until the date of documented SD or Non-CR/Non-PD should be ≥ 7 weeks
- Clinical Benefit Rate (CBR): defined as the percentage of subjects with measurable disease who have a BOR of CR or PR or durable SD lasting ≥ 23 weeks or subjects with evaluable disease who have a BOR of CR or durable Non-CR/Non-PD lasting ≥ 23 weeks
- TTP: defined as the time from the date of the first administration of study drug until the date of first documentation of PD.
- PFS: defined as the time from first dose to documented date of PD or death (whichever occurs first)
- Safety endpoints:
 - Adverse events (AEs), serious AEs (SAEs), clinical laboratory values, vital signs, 12-lead electrocardiograms (ECGs), urine dipstick, occult blood in stool, echocardiogram, Lansky play scores or Karnofsky performance status (KPS), physical examination findings, and height, and closure of proximal tibial growth plates during treatment and follow-up.
 - Plasma lenvatinib exposure parameters
 - Assessment of blood or tumor biomarkers that correlate with clinical response to lenvatinib treatment or AEs associated with lenvatinib treatment
 - Palatability and acceptability of the suspension formulation of lenvatinib

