8 DEFINITIONS AND CONVENTIONS FOR DATA HANDLING

8.1 Visit Windows

Visit windows will be defined to be upper and lower bounds of 1 day of the scheduled visit, following the protocol, which states that efforts should be made to conduct laboratory assessments and administer treatment on the day scheduled (± 1 day).

Tumor assessments for efficacy analysis are to be performed every 8 weeks (within Week 8) for Cohorts 1, 2A and 2B and every 6 weeks (within Week 6) for Cohort 3A and 3B (or sooner if clinically indicated) until documentation of PD.

In the calculation of descriptive statistics for laboratory values and vital signs, if a visit has multiple observations, the observation closest in date and time to the target visit day will be used in the analysis. If 2 or more observations have the same distance to the target visit day, the one that has the highest CTCAE grade or is farthest outside the normal range will be used. The purpose of this windowing is to provide a single record per subject per visit for the calculation of descriptive statistics and change from Baseline per visit. Other safety analyses (e.g., worst grade for laboratory results) will include all observations. All by-visit analyses will be performed using assessments at corresponding scheduled visits recorded in the eCRF. Data from all postbaseline assessments including those at scheduled and unscheduled visits will be used in the shift tables.

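### The 7-week minimum for stable disease fits the 8-weekly scans of Cohorts 1, 2A and 2B but not the 6-weekly scans of Cohorts 3A and 3B, so the SD route to disease control opens about 4 weeks later in the combination cohorts

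*SAP*

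**What the plan says.** **The minimum.** SAP 5.1.2 defines DCR for all cohorts together and adds a condition that begins "To be assigned a BOR of SD or Non-CR/Non-PD, the time from the first administration of study drug until the date of documented SD"; the interval so defined has to reach 7 weeks, for SD and Non-CR/Non-PD alike. SAP 13.2 repeats the 7 weeks for DCR. Protocol 9.7.1.1 and the synopsis state it again for Cohorts 3A and 3B in particular. Protocol Appendix 1 says that "the minimum duration of stable disease is 7 weeks following the date of first dose of study drug", with no exception by cohort.

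**The scans.** SAP 8.1 schedules tumor assessments "every 8 weeks (within Week 8) for Cohorts 1, 2A and 2B", but those of the combination cohorts "every 6 weeks (within Week 6) for Cohort 3A and 3B". Protocol Table 8 (Cohorts 2A/2B) says that scans "should be performed every 8 weeks (within week 8) from C1D1 during the Treatment Phase". Table 9 (Cohorts 3A/3B) says that they "should be performed every 6 weeks (within Week 6) from C1D1 during the Treatment Phase". Protocol 9.5.1.3 keeps this calendar even when treatment is delayed.

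**Rules that do follow the scan schedule.** SAP Table 3 uses 125 days for 8-weekly cohorts and 97 days for 6-weekly cohorts to define more than one missed assessment. SAP 5.4.2.1 uses 16 weeks for Cohort 2B and 18 weeks for Cohort 3B in defining PFS-4 evaluability.

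**The concern.** A 7-week minimum sits one week below the first scan of an 8-weekly schedule, so SD at that scan counts. On a 6-weekly schedule the first scan comes before the minimum and the second comes well after it.

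Two subjects show the effect, both followed only by scheduled scans. A Cohort 2B subject with SD at Week 8 and PD at Week 16 is a disease-control success. A Cohort 3B subject with SD at Week 6 and PD at Week 12 is a failure. Both tables would carry the same label of SD for at least 7 weeks.

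DCR and BOR are named secondary efficacy endpoints for Cohorts 3A and 3B. The stake is a DCR that understates disease control on the combination, a BOR table with too few subjects in the SD category, and a label that hides a different hurdle in each group of cohorts.

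**Working it through.** **1. Reproduce the SAP's own schedule-based figures (SAP Table 3).**
(8+1) × 2 × 7 − 1 = 125 days; (6+1) × 2 × 7 − 1 = 97 days. Both agree with the SAP. The 7-week minimum is a definition, so it has no figure to reproduce.

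**2. Place the scans against 49 days.** Week w runs from Day 7(w−1)+1 to Day 7w, and time elapsed since first dose is the day number minus 1.

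| Scan | Days | Days elapsed | Reaches 49? |
|---|---|---|---|
| Cohorts 3A/3B, first (Week 6) | 36–42 | 35–41 | No |
| Cohorts 3A/3B, second (Week 12) | 78–84 | 77–83 | Yes |
| Cohorts 1/2A/2B, first (Week 8) | 50–56 | 49–55 | Yes |

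If the ±1 day visit window of SAP 8.1 also applies to scans, a Week 6 scan reaches 42 days at most, still 7 short. A Week 8 scan taken on Day 49 has 48 days elapsed and misses by 1.

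**3. Check the companion threshold.** CBR requires 23 weeks (161 days). Week 24 is a scan week on both schedules: Days 162–168, or 161–167 elapsed. So 23 weeks fits both schedules, and 7 weeks fits only one.

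**4. Size, as an illustration.** The documents give no PFS curve, so exponential PFS is an assumption. The range 25% to 50% for PFS-4 is the null and target rate for Cohort 3B (SAP 4). With 1 month = 30.4375 days (SAP 8.3.2), 4 months = 121.75 days = 17.39 weeks, and S(w) = p^(w/17.39).

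| PFS-4 (p) | S(6) | S(8) | S(12) | S(8)−S(12) | S(6)−S(12) | S(6)−S(8) |
|---|---|---|---|---|---|---|
| 50% | 0.787 | 0.727 | 0.620 | 0.107 | 0.167 | 0.060 |
| 25% | 0.620 | 0.529 | 0.384 | 0.144 | 0.236 | 0.091 |

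- S(8)−S(12) is the effect of a 12-week rather than 8-week hurdle: 11 to 14 points, or 0.107 × 18 = 1.9 to 0.144 × 18 = 2.6 of the 18 planned lenvatinib-naïve subjects in Cohort 3B.
- S(6)−S(12) is the share progression-free at Week 6 who progress or die by Week 12: 17 to 24 points, or 0.167 × 18 = 3.0 to 0.236 × 18 = 4.2 subjects. This is a ceiling on those whose Week 6 SD is set aside.
- S(6)−S(8) is the gap that would remain if Week 6 counted in 3A/3B and Week 8 in the other cohorts: 6 to 9 points.

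All three treat everyone without progression as SD. Responders and off-schedule scans reduce the first two.

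**The case against.** The strongest defence is that 7 weeks is a prespecified, uniform minimum, stated for 3A/3B in particular, and that it errs on the conservative side by making combination disease control harder to claim. DCR is descriptive, no test or decision uses it, and the plan makes no formal comparison between cohorts. Cohort 2B and Cohorts 3A/3B are non-randomised and differ by candidacy for ifosfamide and etoposide. This limits the consequence but does not remove the mismatch. Neither document gives a reason for a 12-week hurdle, and the SAP adapts neighbouring rules to the scan interval.

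Appendix 1 and SAP 13.2, read alone, could mean that SD must last 7 weeks, counted up to progression. SAP 5.1.2 and Protocol 9.7.1.1 instead count to the date on which SD was documented, which is the operative definition. The two wordings should be aligned.

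A reader might also infer more than the documents support:

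- *That SD at Week 6 can never lead to disease control, or that DCR as a whole needs 12 weeks in 3A/3B.* SD at Week 6 and again at Week 12 gives a BOR of SD. A late first scan, a clinically prompted scan or the off-treatment scan required by Table 9 can qualify if it shows SD at 49 days or later. CR and PR carry no 7-week condition, and a response first seen at Week 6 can be confirmed from about Week 10.
- *That the 17 to 24 points measure the disadvantage against Cohort 2B.* They compare Week 6 with Week 12 within the combination cohorts; the contrast with an 8-week hurdle is 11 to 14 points.
- *That BOR of PD or NE is inflated.* Neither document says which category receives SD recorded before the minimum.

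Finally, SAP 3.4.2 reports the Cohort 3A recommended dose as already determined, in an open-label study with investigator-assessed response. A definition relaxed only for the combination at that stage needs to be visible. That objection stands and shapes the fix.

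**Conclusion.** The mismatch is real and rests on calendar arithmetic alone: no Week 6 scan reaches 49 days, while scans on Days 50–56 do. On scheduled scans, the SD and Non-CR/Non-PD route to disease control opens at Week 12 in 3A/3B and at Week 8 elsewhere. Subjects are lost when SD at Week 6 is followed by PD, death or no further scan before a qualifying assessment.

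The size estimates (11 to 14 points for the difference in hurdle, and at most about 3 to 4 of 18 subjects affected within Cohort 3B) depend on exponential PFS and on the assumed range for PFS-4, and they shrink with responders or off-schedule scans. Only DCR and the SD and Non-CR/Non-PD categories of BOR are touched. The point should be corrected, but it does not bear on the primary conclusions.

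**What to change.** Before database lock, in SAP 5.1.2 and 13.2, with matching wording in Protocol 9.7.1.1, the synopsis and Appendix 1:

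1. Set the SD and Non-CR/Non-PD minimum at the first scheduled scan minus 1 week: at least 7 weeks for Cohorts 1, 2A and 2B, and at least 5 weeks for Cohorts 3A and 3B.
2. State how days are counted, so that a scan 1 day early is handled. Counting elapsed days, a scan on Day 49 (8-weekly) or Day 35 (6-weekly) misses by 1; counting the day of first dose as 1, it passes.
3. State which BOR category receives SD documented before the minimum.
4. Report DCR and BOR for 3A/3B under the present 7-week rule beside the new result, as a sensitivity analysis.
5. Footnote the tables: the minimum follows the scan schedule, and DCR is not directly comparable between single-agent and combination cohorts. The change reduces the gap and reverses it. Under the same assumption about 6 to 9 points then favour the combination.

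The cost is wording, one derivation parameter and one extra display; no new data are needed.

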3.3.4 Treatment Phase

In all the cohorts, lenvatinib is administered daily (QD) and 1 treatment cycle is defined as a 28-day period for Cohorts 1, 2A, and 2B and a 21-day period for Cohorts 3A and 3B. A new treatment cycle begins every 28 days for Single-Agent Cohorts 1, 2A, and 2B or 21-day period for Combination-Treatment Cohorts 3A and 3B, irrespective of dose interruptions. See Protocol Section 9.4.1 for rules regarding the calculation of lenvatinib dose based on body surface area (BSA).

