5 STATISTICAL METHODS

All descriptive statistics for continuous variables will be reported using n, mean, SD, median, 25th percentile (Q1), 75th percentile (Q3), minimum and maximum. Categorical variables will be summarized as number (percentage) of subjects. The statistical analyses of the study data as described in this section will be performed as further outlined in this SAP, which will be finalized before database lock and be included in the CSR.

Efficacy will be evaluated based on the Full Analysis Set (see SAP [Sections 5.2.1](#) and [7.2](#)). Each cohort will have its own cutoff date for the final analysis for CSR reporting purposes. For Cohorts 1 and 3A, the data cutoff will occur when the RD is determined and the last enrolled subject completes 6 cycles of treatment or discontinues before the end of Cycle 6, whichever occurs first or pending discussion with the PSC. For DTC and osteosarcoma subjects in Cohorts 2A, 2B, and 3B, the cutoff will be after all subjects enrolled have either completed 6 cycles or have discontinued treatment before the end of Cycle 6, whichever occurs first.

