5.4.2.2 Secondary Efficacy Analyses

The secondary efficacy endpoints include BOR over the treatment period (except for Cohort 2A), ORR (except for Cohort 2A), DCR, and CBR, as well as DOR (measurable disease only). PFS and TTP are defined in SAP [Section 5.1](#) and will be performed for subjects in the Full Analysis and Per Protocol Analysis Sets.

Subjects who do not have a tumor response assessment for any reason will be considered nonresponders and will be included in the denominator when calculating the response rate. The count and percentage for ORR will be summarized by dose level for Cohorts 1 and 3A and by cohort for Cohorts 2B and 3B. ORR and corresponding 95% CI based on the exact binomial distribution will be estimated for all corresponding treatment cohorts.

The count and percentage for both the DCR and CBR will be summarized for each treatment cohort, along with the exact 95% CI for.

The median and quartiles of DOR will be estimated by the Kaplan-Meier (KM) method ([Kaplan and Meier, 1958](#)), and the 95% CI estimated with a generalized Brookmeyer and Crowley method ([Brookmeyer and Crowley, 1982](#)).

For PFS, if a subject has not experienced PD or death, then the subject's data will be censored on the date of the last adequate radiologic assessment.

TTP will be calculated using data from all subjects in the Full Analysis Set. The calculation for TTP does not classify deaths as events.

The PFS censoring rules in this SAP and definition of progression date follow the [Food and Drug Administration \(FDA\), Guidance for Industry Clinical Trial Endpoints for the Approval of Cancer Drugs and Biologics \(2007\)](#) (See SAP Table 3). The PFS censoring rules are referenced in SAP Table 3 and TTP censoring rules are referenced in SAP Table 4.

Table 3 Censoring Rules for Analysis of Progression-Free Survival

No	Situation	Date of Progression or Censoring	Outcome
1	No baseline tumor assessments	Date of first dose	Censored
2	No postbaseline tumor assessments	Date of first dose	Censored
3	Progression documented between scheduled visits	Date of first radiologic PD assessment	Progressed
4	More than 1 NE tumor timepoint assessment	Date of last adequate radiologic assessment before NE tumor assessments	Censored
5	No progression at time of data cutoff	Date of last adequate radiologic assessment	Censored
6	New anticancer treatment started	Date of last adequate radiologic assessment prior to or on date of new anticancer treatment	Censored

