CBR	Full Analysis Set	Number (percent) of subjects (measurable disease with CR+ PR + SD \geq 23 weeks, evaluable disease with CR + Non-CR/Non-PD \geq 23 weeks) and its exact 95% CI using method of Clopper and Pearson.	Investigator

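### In Cohorts 3A and 3B, a cutoff at or near the earliest date the plan permits (18 weeks after the last first dose) would count late-enrolled, still-stable subjects as lacking the 23 weeks that CBR requires

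*SAP*

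**What the plan says.** SAP 5.1.2 gives one CBR definition for all cohorts. It covers subjects with measurable disease "who have a BOR of CR or PR or durable SD lasting ≥ 23 weeks" and subjects with evaluable disease who have CR or Non-CR/Non-PD for the same 23 weeks. CR and PR count at any duration.

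SAP 5.4.2.2 states: "The count and percentage for both the DCR and CBR will be summarized for each treatment cohort", with an exact 95% CI. The CBR row of SAP 13.2 begins "Number (percent) of subjects (measurable disease with CR+ PR + SD", repeats the 23 weeks and names the Full Analysis Set. That set (SAP 5.2.1) is everyone enrolled who passed screening, with no minimum follow-up.

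The cutoff is set in cycles (SAP 5). For the three expansion cohorts, 3B included, "the cutoff will be after all subjects enrolled have either completed 6 cycles or have discontinued treatment before the end of Cycle 6". For 1 and 3A "the data cutoff will occur when the RD is determined and the last enrolled subject completes 6 cycles of treatment", or that subject stops before the end of Cycle 6, or subject to discussion with the steering committee. A cycle is 28 days in Cohorts 1, 2A and 2B and "a 21-day period for Cohorts 3A and 3B" (SAP 3.3.4), and dose interruptions do not lengthen it. Scans in 3A and 3B "should be performed every 6 weeks (within Week 6) from C1D1 during the Treatment Phase" (Protocol Table 9, footnote o).

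**The concern.** A six-cycle cutoff is 24 weeks in the single-agent cohorts but 18 weeks in the combination cohorts, while the CBR threshold is 23 weeks in both. A combination subject enrolled near the end, still on treatment and still stable at an 18-week cutoff, has not failed the criterion. The time needed to meet it has simply not passed.

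The plan handles this situation for PFS: without progression or death, the "data will be censored on the date of the last adequate radiologic assessment". CBR has no corresponding rule, and SAP 7 (changes in the planned analyses) adds none. At stake is whether the reported CBR in 3A and 3B is lowered by short follow-up rather than by progression, with nothing beside it in the table to tell the two apart.

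**Working it through.** The plan gives no figure to reproduce, since the cutoff is never stated in weeks. As a check on the calendar, the SAP's own missed-assessment windows reproduce: ((6+1)×2×7)−1 = 97 days and ((8+1)×2×7)−1 = 125 days.

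**1. Calendar.** Stable disease is counted from first dose.

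| | Six cycles | 23 weeks | Difference |
|---|---|---|---|
| 28-day cohorts | 6×28 = 168 d (24 wk) | 161 d | 7 d to spare |
| 3A, 3B | 6×21 = 126 d (18 wk) | 161 d | 35 d short |

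**2. Scan grid.** Scheduled scans in 3A and 3B fall in Weeks 6, 12, 18 and 24. The first that can show 23 weeks is in Week 24 (days 162 to 168). The end of that week is 167 elapsed days, and 167 − 126 = 41. With a day-126 cutoff, a still-stable subject first dosed less than 35 days before the last one cannot have qualified. Between 35 and 41 days it depends on the scan date.

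**3. Late subjects in 3B.** There are 18 planned (SAP 4). Accrual time is not given, so even accrual over 6, 12 or 24 months is assumed. First doses are then 10.7, 21.5 or 43.0 days apart, which puts 4, 2 or 1 subjects (the last included) within 35 to 41 days of the last.

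**4. Chance that such a subject would have reached 23 weeks progression-free.** Assume exponential PFS, S(t) = p^(t/121.75), where 4 × 30.4375 = 121.75 days (SAP 8.3.2) and p is PFS-4 at the target or null value for 3B (SAP 4):
- p = 0.50: S(161) = 0.400
- p = 0.25: S(161) = 0.160

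Taking 4 months as 126 days (18 weeks) instead gives 0.412 and 0.170.

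**5. Expected number counted as not benefiting only for lack of follow-up, with no responders.**
- Smallest: 1 × 0.160 = 0.16 subject; 0.16/18 = 0.9 points.
- Largest: 4 × 0.400 = 1.60 subjects; 1.60/18 = 8.9 points.
- At 12 to 24 months' accrual: 0.16 to 2 × 0.400 = 0.80, less than one subject.

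Each whole subject moves CBR by 1/18 = 5.6 points. Any late subject who has responded is already in the numerator, so these figures fall when there are responders among the late progression-free subjects.

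**6. Cohort 3A, illustration only.** Twelve subjects over 24 months give 1 late subject and 0.16/12 = 1.3 points. Twenty-four over 6 months give up to 6 late subjects and 2.40/24 = 10.0 points. Subjects in 3A are assigned in sixes with Cycle 1 toxicity review between groups, so even accrual fits poorly. The day-126 cutoff is also not a floor there, because the last enrolled subject may stop early.

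**The case against.** A reader might infer that CBR in 3A and 3B will be biased. The documents do not support that. For 3B the cutoff comes after the six-cycle condition is met, with no upper limit, and for 3A the steering committee may discuss it. A cutoff five to six weeks later complies with the plan and removes the problem in 3B. Nothing requires it, however.

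Nor does the SAP say in words that such subjects are failures. This follows from the definition and a denominator without a follow-up condition. SAP 5.4.2.2 makes subjects without a response assessment nonresponders but does not address stable subjects with short follow-up.

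It can also be said that short follow-up is visible elsewhere. SAP 5.4.2.2 plans Kaplan-Meier PFS with 4- and 12-month rates and reversed-censoring follow-up times, and SAP 13.2 adds a PFS plot. These show that follow-up is limited, but they neither correct the CBR percentage nor count the subjects concerned.

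Finally, the direction is conservative, CBR carries no test or decision rule, and the shift is small beside the exact interval (6/18 = 33%, 95% CI 13 to 59). That stands, and it is why the point is minor.

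**Conclusion.** The mismatch is real: 126 days against 161 in the 21-day cohorts. If the cutoff is at or near the earliest permitted date, subjects in 3A and 3B who started late and are still stable count as not benefiting. For 3B the expected size is about 0.2 to 1.6 of 18 subjects (1 to 9 points of CBR). That rests on assumed even accrual over 6 to 24 months, exponential PFS, a day-126 cutoff and no responders, and it is smaller if any of these late progression-free subjects have responded.

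The 35-to-41-day window should not be read as a bound for 3A. If the last enrolled subject discontinues early, others may have less than 18 weeks. Cohort 1 shares that clause, so its 168 days are not guaranteed either. In 2A and 2B, on the SAP's wording, anyone still on treatment has at least 168 days.

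A reader might also infer that the main efficacy result is weakened. It is not: PFS-4 in 3B and the recommended dose in 3A do not use the 23-week criterion. The effect is confined to one descriptive secondary endpoint.

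**What to change.** Keep CBR on the Full Analysis Set as planned. In SAP 5.4.2.2 and 13.2, before database lock, add for 3A and for 3B (lenvatinib-naïve subjects in 3B):

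1. The number of subjects still in SD or Non-CR/Non-PD with less than 23 weeks of follow-up at cutoff.
2. As a supportive row, CBR with exact 95% CI among subjects first dosed at least 168 days (24 weeks) before cutoff, whatever their outcome, using the enrollment date for anyone never dosed. Selecting on start date alone keeps outcome out of the selection, and 168 days allows the Week 24 scan.

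The cost is one count and one row, with no protocol amendment and no change of cutoff. The supportive row has a smaller denominator and a wider interval. At the fastest assumed accrual, with no CBR success among the four late subjects, it would read 6/14 = 43% (95% CI 18 to 71) beside the planned 6/18 = 33% (13 to 59). Slower accrual, or a late responder, narrows that gap. If only one item is adopted, the count is the more useful.
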